6.6. Dose Modification

This is not applicable in this study.

6.7. Treatment of Overdose

For this study, any dose of study drug administered as part of the study greater than the dose prescribed by the protocol will be considered an overdose.

In the event of an overdose, the PI/investigator should:

1. Contact the medical monitor immediately.
2. Closely monitor the participant for any AE/SAE and laboratory abnormalities possibly associated with overdose and the participant will be clinically followed up until any AE/SAE has resolved.
3. Obtain a plasma sample for PK analysis approximately 4 hours after study drug administration.
4. Document the quantity of the excess dose as well as the duration of the overdose in the eCRF.

The sponsor is responsible for notifying the MHRA and Research Ethics Committee (REC) of the potential serious breach within 7 days of becoming aware of it.

7. Discontinuation of Study Intervention/Withdrawal

7.1. Participant Withdrawal

A participant may withdraw their consent to participate in the study at any time, for any reason, without prejudice to his/her future medical care. Participants may decline to give a reason for their withdrawal. Additionally, the PI/investigator may withdraw a participant if, in their clinical judgement, it is in the best interest of the participant or if the participant cannot comply with the protocol. Wherever possible, the tests and evaluations listed for the early withdrawal visit should be carried out, and if clinically indicated, the participant should be invited back for a final follow-up visit.

The sponsor should be notified of all study withdrawals in a timely manner, and in cases where the withdrawal is due to a medical reason the participant would be referred to his/her GP.

Participants will be counselled that early withdrawal from the HVC phase of the study is strongly discouraged, as it may pose a risk both to the participant and his/her contacts. In the event of a participant insisting on early withdrawal during the quarantine isolation period, the participant will be encouraged to stay and would be advised of the potential risks of carrying RSV infection into the community, and to vulnerable groups in particular as described in [Section 2.5.1.1, Vulnerable Persons](#).

If the participant withdraws consent for disclosure of future information, the sponsor may retain and continue to use any data collected before such a withdrawal of consent.

If a participant withdraws from the study, he/she may request destruction of any samples taken and not tested, and the PI/investigator must document this in the site study records.

7.2. Participant Discontinuation

Enrolled participants will be discontinued from study drug receipt for any of the reasons listed below. These participants must not receive any additional intervention but should continue to be followed for safety. Additional unscheduled visits may be performed for safety reasons.

- Noncompliance with the study requirements and restrictions.
- Clinically significant abnormal laboratory findings, which in the opinion of the PI/investigator and/or sponsor precludes further participation in the study.
- Development of intercurrent illness, which in the opinion of the PI/investigator would compromise the health of the participant or the study objectives.
- The PI/investigator's decision that withdrawal from further participation would be in the participant's best interest.
- Termination of the study at the discretion of the PI/investigator or sponsor for safety, behavioural, or administrative reasons.
- The wish of the participant.
- Any intervention-related SAEs.
- Anaphylactic reaction following dosing.

- The participant becomes pregnant (if pregnancy is specified as an exclusion criterion).

Enrolled participants who are withdrawn from the study, will be requested to attend an early withdrawal visit, with assessments as detailed in the SoE.

7.2.1. Temporary Discontinuation/Temporary Delay in Enrolment

If a participant is found to be ineligible due to transient circumstances (such as acute disease and/or fever) at the quarantine admission, inoculation with challenge agent will be postponed until the transient circumstances have been resolved and the participant may be re-invited to a later quarantine group within the allowed time window. For participant rescreening refer to [Section 5.4](#), Screen Failures.

7.3. Lost to Follow-up

A participant will be considered lost to follow-up if he/she repeatedly fails to return for scheduled visits and is unable to be contacted by the study site.

The following actions must be taken if a participant fails to return to the study site for a required study visit:

- The site must attempt to contact the participant and reschedule the missed visit as soon as possible and counsel the participant on the importance of maintaining the assigned visit schedule and ascertain whether the participant wishes to and/or should continue in the study.
- Before a participant is deemed lost to follow-up, the PI/investigator or designee must make every effort to regain contact with the participant (where possible, 3 telephone calls and, if necessary, a follow-up letter to the participant's last known mailing address or local equivalent methods). These contact attempts should be documented in the participant's medical record.
- Should the participant continue to be unreachable, he/she will be considered to have withdrawn from the study.

Discontinuation of specific sites or of the study as a whole are handled as part of [Appendix 1](#), Regulatory, Ethical, and Study Oversight Considerations.

7.4. Participant Replacement Strategy

Participants may be replaced in this study.

If a participant discontinues from study intervention OR withdraws from the study for reasons not related to AEs, a replacement participant may be enrolled if deemed appropriate by the investigator and sponsor. The replacement participant will generally receive the same intervention as the participant being replaced. The replacement participant will be assigned a unique treatment/randomisation number equalling the randomisation number of the replaced participant, plus 100. This will ensure that the replacement participant receives the same allocated, blinded treatment as the participant who is being replaced.

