6.3. Randomisation and Blinding

hVIVO assigns a unique 6-digit number to each participant in the hVIVO database. This number will be used to identify a participant up to the point of randomisation, on source documents, on all study correspondence and in the study database. A separate randomisation number will be allocated to the

participants at randomisation and will be used for allocation to a study arm. The randomisation number encodes the participant's assignment to 1 of 2 study arms (RV299/placebo) in a 1:1 ratio.

Randomisation numbers will be assigned sequentially in ascending order; and once assigned, that randomisation number shall not be reassigned. The study site will keep a log of the randomisation number assigned to each participant.

A designated unblinded statistician, separate from the conduct or analysis of the study, will be responsible for the computer-generated randomisation schedule. Sealed copies of the randomisation code will be stored in a secure location.

Randomisation numbers will follow a 3-digit format e.g., [001]. If participants are replaced as per [Section 7.4](#), Participant Replacement Strategy, the replacement participant will be assigned a new, unique randomisation number equalling the randomisation number of the replaced participant, plus 100. This will ensure that the replacement participant receives the same allocated, blinded treatment as the participant who is being replaced.

A copy of the randomisation code list will be sent to the unblinded pharmacist/designee preparing the IMP, so that IMP can be prepared for each participant as appropriate. An independent statistician prepares the randomisation schedule, and the GMP pharmacy provider's pharmacist/designee will prepare the participant level IMP doses in line with the randomisation schedule.

Each participant will be dispensed blinded IMP, labelled with his/her unique randomisation number, throughout the study. With the exception of the unblinded pharmacist, unblinded IMP management personnel at the clinical site, the unblinded statistician preparing the randomisation code list, and the quality assurance auditors where necessary, the PI/investigator and all other clinical and nonclinical staff, (including the study statistician, data management staff), and the participants will remain blinded to the treatment allocation until after the database has been locked and approval for study unblinding has been given.

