Following database lock, on receipt of authorisation from the sponsor, a copy of the randomisation code list will be provided to the study statistician to conduct study unblinding prior to analysis.

The PI/investigator will be provided with a tamper-evident sealed envelope containing details of the treatment for each participant. All opened and unopened envelopes will be collected or destroyed after the end of the study, as agreed with the sponsor.

Individual emergency code break envelopes will be provided to the PI/investigator should it be necessary to break the blind for a participant. The PI/investigator will ensure there is an appropriate procedure in place to allow access to the code break envelopes in case of an emergency arising during the quarantine period, as per hVIVO's SOPs. An emergency means that the relevant medical decision on the further care of a participant is dependent on the actual identity of the study treatment that the participant has received.

The emergency code break envelopes will contain details of the treatment for each participant.

When the code break envelope is opened, the PI/investigator must note the date, time, reason for unblinding and the details of the PI/investigator and or designated site staff that broke the blind and record this information according to hVIVO SOPs. The PI/investigator must also immediately notify the sponsor's medical monitor that the code has been broken. If possible, the sponsor should be consulted before the code is broken, but this will only occur if the safety of the participant will not be compromised.

Even if the code is broken, blood samples for safety, efficacy, PK, and other assessments will continue to be drawn for the remainder of the planned study period following the last dose if doing so will not compromise participant welfare.

Dosing with IMP must be discontinued after unblinding, but the participant will be followed up until resolution of any AEs.

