7.6. Adaptive Features

This study is designed to be able to utilise adaptive features to enhance study safety, efficiency, and efficacy. These design elements are predefined in their scope and limit, as detailed in [Table 7-2](#)

The implementation of study-specific adaptive features will be documented in a non-substantial amendment. Generic adaptive features may be implemented at any time at the discretion of the PI/investigator.

Table 7-2: Adaptive Features

Adaptive Design Category	Feature	Limit
Generic		
Cohort(s)	
 Participants who have been withdrawn (for any reason) may be replaced (sponsor and/or PI discretion). Participants who are replacing a withdrawn participant may be randomised for inclusion, and dosed/challenged: 
 In an ongoing cohort In a new cohort Separately. Any study cohort may run at the same time 	
 The stopping rules of the study must be always adhered to, and replacement participants may not be enrolled to replace participants who have been withdrawn from the trial due to the meeting of stopping rules. Replacement participants will be given replacement randomisation numbers (see Section 7.4, Participant Replacement Strategy). All protocol-defined rules and safety criteria must be met before any study part, cohort, or participant commences the study.
Sample/specimen	
 The PI/investigator may perform additional safety assessments, at any time, if they believe them to be clinically required. Where clinically required (sponsor and/or PI discretion), participants may be referred for consultation(s) and/or investigation(s) under the care of a specialist physician. 	
 The maximum blood volume will not be exceeded. Any required additional safety assessments, or specialist referrals, will be conducted on a case-by-case basis. As such the maximum number needed cannot be prospectively defined.

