6.2. Randomisation / Treatment Allocation and Blinding

hVIVO assigns a unique 6-digit number to each participant in the hVIVO database. This number will be used to identify a participant up to the point of randomisation, on source documents, on all study correspondence, and in the study database. A separate randomisation number will be allocated to the participants at randomisation and will be used for allocation to a study arm. The randomisation number encodes the participant's assignment to 1 of 2 study arms (RV299/placebo) in a 1:1 ratio.

Randomisation numbers will be assigned sequentially in ascending order, and once assigned, that randomisation number will not be reassigned. The study site will keep a log of the randomisation number assigned to each participant.

A designated unblinded statistician, separate from the conduct or analysis of the study, will be responsible for the computer-generated randomisation schedule. Sealed copies of the randomisation code will be stored in a secure location.

Randomisation numbers will follow a 3-digit format e.g., 001. If participants are replaced as per Section 7.4, Participant Replacement Strategy, the replacement participant will be assigned a new, unique randomisation number equalling the randomisation number of the replaced participant, plus 100. This will ensure that the replacement participant receives the same allocated, blinded treatment as the participant who is being replaced.

A copy of the randomisation code list will be sent to the unblinded pharmacist/designee preparing the IMP, so that IMP can be prepared for each participant as appropriate. An independent statistician prepares the randomisation schedule, and the GMP pharmacy provider's pharmacy/designee will prepare the participant level IMP doses in line with the randomisation schedule.

Each participant will be dispensed blinded IMP, labelled with his/her unique randomisation number, throughout the study. With the exception of the unblinded pharmacist, unblinded IMP management personnel at the clinical site, the unblinded statistician preparing the randomisation code list, and the quality assurance auditors where necessary, the PI/investigator and all other clinical and nonclinical staff, (including the study statistician, data management staff), and the participants will remain blinded to the treatment allocation until after the database has been locked and approval for study unblinding has been given.

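### The replacement numbering has no exception for a broken code, so an investigator who opened the envelope could know a replacement's arm; the rules on who may be replaced also conflict

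*Protocol*

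**What the plan says.** **Numbering.** Protocol 6.3 gives a replacement a "number equalling the randomisation number of the replaced participant, plus 100", and SAP 6.2 repeats the rule: "the replacement participant will be assigned a new, unique randomisation number equalling the randomisation number of the replaced participant, plus 100". Protocol 7.4 first says "The replacement participant will generally receive the same intervention as the participant being replaced" and then, in the same paragraph, "This will ensure that the replacement participant receives the same allocated, blinded treatment as the participant who is being replaced".

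**Code break.** Under Protocol 6.3 the investigator holds individual envelopes that state each participant's treatment. After one is opened, "Dosing with IMP must be discontinued after unblinding, but the participant will be followed up until resolution of any AEs". The sponsor's medical monitor must be told that the code was broken. No section says how replacement or numbering works after that.

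**Who may be replaced.** The synopsis and Protocol 7.4 cover a participant who discontinues study intervention or "withdraws from the study for reasons not related to AEs, a replacement participant may be enrolled", if the investigator and sponsor think it appropriate. Table 7-2 in Protocol 7.6 says "Participants who have been withdrawn (for any reason) may be replaced (sponsor and/or PI discretion". Its only bar is on replacing people withdrawn because stopping rules were met, and it refers back to 7.4 for numbering.

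**The concern.** Linking a replacement to the same arm is harmless while the code is intact, because nobody at the site learns anything from the link. Once the first participant's envelope has been opened, the same link discloses the second participant's arm. The investigator who opened the envelope is also one of the people who decide whether to replace.

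Ordinary numbers are issued in ascending sequence (Protocol 6.3). The plus-100 number stands outside that sequence, and no rule says which inoculated participant receives it. The synopsis and the schedule of events place randomisation after inoculation, at a time that depends on the qicPCR result. The recipient could therefore be chosen with the arm known and with time to positivity in view. The investigator's later judgements on adverse-event causality for that participant would not be blind either. Protocol 6.3 itself requires the investigator to stay blinded until database lock.

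The conflict over eligible reasons is a separate matter and needs no code break. Two sites or two cohorts could follow different sections and replace different people.

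**Working it through.** No sample-size or power figure bears on this point, so there is no plan figure to reproduce. The check is a comparison of the rules plus simple arithmetic.

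**1. Does the link identify the arm?** Assume the first 80 numbers are 001 to 080 (the documents give only a three-digit format and a total of 80). Adding 100 gives 101 to 180. The two sets do not overlap, so each replacement number points to exactly one replaced number. The site keeps the log of numbers (Protocol 6.3). If the replaced participant's arm is known, the replacement's arm is known with probability 1.0. An independent 1:1 draw would give 0.5.

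**2. Is replacement open after a code break?** A code break during dosing forces discontinuation of study drug, which is the first limb of 7.4. It does not withdraw the participant: 6.3 continues sampling and follow-up. Whether the non-AE condition in 7.4 covers both limbs or only withdrawal is unclear, so both readings are shown.

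| Code break during dosing | 7.4 and synopsis, condition on both limbs | 7.4 and synopsis, condition on withdrawal only | Table 7-2 |
|---|---|---|---|
| AE-related, stays in study | No | Yes | No (not withdrawn) |
| AE-related, also withdrawn | No | Yes | Yes, unless withdrawn under stopping rules |
| Not AE-related | Yes | Yes | Only if also withdrawn |

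The route is open in some cells and closed in others. No cell is closed because the code was broken.

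**3. Size.** The plan has 40 per arm (synopsis; 40 + 40 = 80) and an infection rate of 65% to 85% (Protocol 2.3).

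- One replacement as a share of an arm: 1/40 = 2.5%.
- Infected per arm: 40 × 0.65 = 26 to 40 × 0.85 = 34. One replacement, if infected, is 1/34 = 2.9% to 1/26 = 3.8% of these.
- The documents give no code-break rate. Assuming 0 to 2 such replacements, the share of the planned 80 is 0/80 = 0% to 2/80 = 2.5%.

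**4. The replacement rules side by side.**

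| | Synopsis and 7.4 | Table 7-2 |
|---|---|---|
| Reason | Not related to AEs | Any, except stopping rules |
| Event | IMP discontinuation or withdrawal | Withdrawal |
| Decision | Investigator and sponsor | Sponsor and/or PI |
| Same arm | 'Generally', then 'ensure' | By reference to 7.4 |

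The rows for reason, event and decision differ between sections. The last row is a contradiction inside 7.4.

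**The case against.** The best reply is that this is a rare-event gap. Most emergency code breaks will follow an adverse event, and one reading of 7.4 then bars replacement. That reply stands on frequency: with no code break there is no effect. It does not remove the gap, because the other reading of 7.4 and Table 7-2 leave the route open.

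A reader might also infer several stronger things that the documents do not support:

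- **The replacement always inherits the arm.** The synopsis and 7.4 say 'generally'. The defect is that no exception is defined.
- **The sponsor knows the arm.** Protocol 6.3 has the medical monitor told only that the code was broken. The sponsor can unblind potential SUSARs (10.3.8), but a SUSAR halts dosing under Table 7-1, and Table 7-2 bars replacing those withdrawn under stopping rules.
- **Selection for inoculation is compromised.** Randomisation follows inoculation, and replacements may join an ongoing cohort, so the number need not be attached before challenge.
- **Pregnancy is a ready non-AE route.** After admission, the next scheduled test is at Day 28 or early withdrawal. Dosing starts by the evening of Day 5, and nine further 12-hour intervals (9 × 12 = 108 hours) end it on the morning of Day 10. A Day 28 finding comes after dosing and after the Day 12 efficacy data.
- **Leaving because of RSV illness always counts as non-AE.** Section 10.3.6.2 lets diary symptoms become AEs when they meet the definition and are clinically significant.
- **Efficacy measurement is exposed.** Diary scores are self-reported, and nothing tells the participant the arm. The primary endpoint is a laboratory assay. SAP 10.1.1 lists data after the morning of Day 12 without using them for efficacy, subject to blinded review, so discharge timing has little reach.
- **Replacing AE withdrawals dilutes the safety rate.** If, say, 4 of 40 became 4 of 44 (10.0% to 9.1%), the second figure would be the correct proportion of everyone dosed, as SAP 9.6 defines that population.

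**Conclusion.** The concern holds in limited form. The numbering rule lacks a code-break exception, and this can give an investigator certain knowledge of a replacement's arm. What is exposed is the choice of who receives the linked number and the investigator's causality judgements. The size rests on an assumed count and on replacement actually being chosen; at a count of zero nothing is lost. The contradictions between the synopsis with 7.4 and Table 7-2, and within 7.4, hold on the text alone and need no assumption. Both are worth correcting because the correction is cheap. Neither threatens the primary comparison.

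**What to change.** 1. In Protocol 6.3 and 7.4 and SAP 6.2, state that a participant whose code has been broken is either not replaced or is replaced with a fresh concealed number from a reserve 1:1 list. Keep the plus-100 rule where the code is intact; scrapping it for everyone is not needed.
2. Reconcile the synopsis, 7.4 and Table 7-2 so that they carry one replacement criterion and name one decision-maker. Say whether the non-AE condition applies to IMP discontinuation. Which criterion to adopt is for the sponsor and investigator.
3. Resolve 'generally' against 'ensure' in 7.4, with any exception spelled out.

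The cost is a short amendment and matching SAP text. If the fresh-number option is taken, a small reserve list is also needed, with study drug prepared against it because supplies are labelled by randomisation number. The downside is that the arms may end one or two participants apart.
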